11.3 Statistical Analysis of Translational Studies

A description of the statistical methods for the measurement of the changes in gene expression is also contained in section 9.2.2 through 9.2.4. Analysis will be performed using the CuffDiff2 program, part of a commercially available Cufflinks package that will be used in the analysis of the tissue samples. The software models how variability in measurements of a RNA transcript's fragment count is dependent on both its expression and splicing structure. It fits the observed variance in fragment counts as a function of the mean across replicates. It then estimates the number of fragments that originated from each transcript. The algorithm estimates uncertainty by calculating the confidence that each fragment is correctly assigned to the transcript that generated it. The uncertainty in the fragment's count is then mapped as a beta distribution and the overdispersion in RNA sequences as a negative binomial. The algorithm then mixes the distributions together. The result is a beta negative binomial distribution that reflects both the sources of variability in an isoform's measured expression level. This method is well published and further detail can be found in reference 71.

Expression of genes from patients with pre- and post-radiation will be compared, with a false-discovery rate (FDR) of less than 0.05.

Expression of genes from patients with pathologic complete response versus non-complete responders will be compared using an unpaired t test on all probes, with a false-discovery rate (FDR) of less than 0.05. If <15% complete pathologic responses are seen, then partial responses versus no response will be compared in a similar manner.

REFERENCES

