2.2 Secondary

- 2.2.1 Measure rates of breast fibrosis and pain for patients treated with APBI and compare with historical controls of patients treated with post-operative APBI.
- 2.2.2 Collect data on cosmetic outcomes for patients treated with pre-operative APBI
- 2.2.4 Measure rates of need for re-excision because of a close or positive margin after pre-operative APBI.
- 2.2.5 Record long term outcomes of local recurrence rates and overall survival of patients treated with this modality.
- 2.2.6 Demonstrate the feasibility of MRI-based treatment planning for pre-operative APBI and compare dosimetric data from treatment planning with patients treated on a previous institutional post-op APBI protocol.
- 2.2.7 Study changes in MRI imaging from pre-treatment evaluation, treatment planning, and pre-surgical imaging and correlate those changes to pathological response.
- 2.2.8 Measure changes in tumor gene expression and immune response to radiation therapy and correlate this with pathologic response.

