9.0 Pathologic Evaluation and Genetic Evaluation of Tissue Specimens

9.1 Pathological Evaluation and Immune Biomarkers

- 9.1.1 The surgical specimens will be subject to routine pathological analysis. Remaining tissue from the pre-treatment biopsy, as well as any residual tumor tissue post-RT, will be stored in accordance with MCW department of Pathology guidelines. Routine hematoxyline and eosin (H&E) stain will be used for morphological analysis and for the determination of immune cell infiltrates. The samples will be assessed by the breast pathologist as previously described (65,66). One H&E slide and 20 unstained slides will be reserved for Gene Expression Profiling (described in section 9.2 below).
- 9.1.2 Immune cell infiltrates have previously been shown to correlate with both breast cancer-specific outcomes and response to neoadjuvant treatment (67). We anticipate that enhanced immune cell infiltration (determined as described above in 8.1.1, or with additional immunostains if needed and tissue available allows) will correlate with pathologic responses to RT.
- 9.1.3 Blood specimens (50mL, collected in 10mL lavender top EDTA tubes) will be obtained at the time of routine blood draws: once pre- and once post-radiation, (last day and up to one week after +/- 1 treatment) for future studies of immune markers/peripheral blood cells and other cancer and treatment related biomarkers that will attempt to predict radiation side effects and potentially treatment responses. These samples will be obtained at Froedtert Hospital, and in order to spare patient additional travel, those receiving radiation treatment outside Froedtert may opt out of the blood draw at the end of radiation. These samples will also be stored on the MCW Campus and analysis will be performed on campus. The process for handling specimens will be as follows:
 - 9.1.3.1 After collection, invert tube(s) multiple times to ensure adequate mixing of EDTA. ***Call the co-PI's laboratory ([name]) at [contact] to let them know they need to come pick up the PBMCs. If no answer, call the co-PI at [contact]. The plasma will be processed in the laboratory performing the blood draw, and the PBMCs will be collected by the PI's laboratory member for the remainder of the processing outlined below.**

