9.1.4 Peripheral Blood Analysis

9.1.4.1 Plasma: Plasma samples will be stored at [name] for batched analysis. Plasma will be interrogated for chemokine and cytokine levels using a multiplex platform from Eve Technologies (<https://www.evetechologies.com>).

9.1.4.2 Cryopreserved samples: Cryopreserved samples will be stored [name] for batched analysis. Samples will be thawed and stained with fluorophore-conjugated antibodies against one or more of the following: CD4, CD8, CD25, CD62L, CD45RA, CD127, ICOS, PD-1, PD-L1, FoxP3, CD3, CD56, CD16, CD83, TIM-3, Ki-67, CD19, CD20, CD33, CD15, CD11b, HLA-DR and others. Stained cells will be interrogated by flow cytometry and results analyzed using FlowJo or similar software.

9.1.4.3 RNAlater samples: Cells in RNA later will be stored [name] for batched analysis. Samples will be thawed and RNA will be extracted. The transcriptome will be analyzed by RNA deep sequencing (RNAseq) using the Illumina HiSeq platform. Targeted RT-PCR will be used to validate genes of interest identified by RNAseq. TCR deep sequencing data may also be obtained from the RNAseq.

9.1.5 The evaluating pathologist will assess the percentage of the surgical specimen that contains live tumor.

- 9.1.6 Sections will be subject to immunohistochemical evaluation of the marker Ki-67 pre- and post-operatively to estimate the tumor cell population capable of proliferation after treatment (68). Since the monoclonal antibody Ki-67 detects a nuclear antigen expressed in all phases of the cell cycle except G0, this offers a unique means to assess response to radiotherapy. This approach has never before possible with standard breast radiation treatment, because standardly treatment is delivered after all measurable tumor has been removed.

9.2 Gene Expression Profiling and Advanced Imaging:

- 9.2.1 RNA will be procured using the Tissue Bank quality control measures fixed paraffin embedded tissues pre-radiation (from biopsy) and post-radiation (surgical specimen).

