- 9.2.2 We will perform global gene expression profiling using RNAseq to identify differential expression patterns that correlate with response to radiation. We will utilize the MCW Human and Molecular Genetics Center Sequencing Core to perform RNAseq and analysis. Total RNA will be extracted using Trizol per the MCW Tissue Bank's standard procedure, and the total RNA will be poly-A purified, transcribed, and chemically fragmented using Illumina's TruSeq RNA library kit. Libraries will be prepared for each sample, indexed for multiplexing, and then sequenced on an Illumina HiSeq 2000. Briefly, we will plan to multiplex 4 libraries per lane x 8 lanes per flow cell, enabling us to test 32 samples per flowcell, a setup which has routinely yielded us 150-180 million reads (87.5% mapped reads) per lane. For data analysis, sequencing reads will be demultiplexed and compressed into FASTQ files using CASAVA 1.8 or equivalent software, aligned to the human genome by TopHat (69), and analyzed for transcript abundance using Cufflinks (70). Cufflinks produces FPKM (fragments per Kb of exon per million fragments mapped) values for all transcript isoforms. The CuffDiff2 program (part of Cufflinks package) then statistically analyzes differences in transcript abundance, taking into account variance between biological replicates and correction for false discovery rate (71).
- 9.2.3 Expression of genes from patients with pathologic complete response versus non-complete responders will be compared using an unpaired t test on all probes, with a false-discovery rate (FDR) of less than 0.05. If <15% complete pathologic responses are seen, then partial responses versus no response will be compared.
- 9.2.4 Expression of genes from patients with pre- and post-radiation will be compared, with a false-discovery rate (FDR) of less than 0.05.
- 9.2.5 Gene expression data from this patient group will be compared to previously published gene expression signatures for radiation sensitivity, and OncotypeDx, a metric that predicts chemotherapy response (79,89,90).
- 9.2.6 Correlation of MR parameters and gene expression differences will be performed as described previously (90). Correlation of MRI parameters and CT-imaging with pathologic responses will also be determined.

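### Pre- and post-radiation tumor RNA come from the same patients, but the plan states no pairing and describes its named program, CuffDiff2, without a patient term

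*Combined protocol and SAP*

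**What the plan says.** Secondary objective 2.2.8 reads: "Measure changes in tumor gene expression and immune response to radiation therapy and correlate this with pathologic response".

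Section 9.2.1 gives the source of the tumor RNA as "fixed paraffin embedded tissues pre-radiation (from biopsy) and post-radiation (surgical specimen". Section 9.1.1 says that leftover biopsy tissue, "as well as any residual tumor tissue post-RT, will be stored". This is a single-arm trial in which every patient is biopsied, irradiated and then operated on. Each patient with tumor left after radiation can therefore supply one sample at each time.

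For the pre/post comparison, 9.2.4 and 11.3 use the same sentence: "Expression of genes from patients with pre- and post-radiation will be compared, with a false-discovery rate (FDR) of less than 0.05". It names no test, patient factor or within-patient difference.

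On method, 11.3 says: "Analysis will be performed using the CuffDiff2 program". It says of that program: "It fits the observed variance in fragment counts as a function of the mean across replicates". It then lists two sources of variability: uncertainty in assigning fragments to transcripts, and overdispersion of the counts. Section 9.2.2 says: "The CuffDiff2 program (part of Cufflinks package) then statistically analyzes differences in transcript abundance, taking into account variance between biological replicates". Neither section mentions patient, block or pair.

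**The concern.** A change in expression within a tumor is a within-patient quantity. If a patient's two samples are correlated, differences between patients cancel when each patient is compared with herself, and the error term should reflect that. If the samples are instead treated as replicates in a pre group and a post group, between-patient variation stays in the error term. Real changes then fail to reach the FDR threshold.

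What is at stake is the yield of objective 2.2.8 and of the later steps in 9.2 that use genes found to change. Gene expression is not in the 11.2 list of secondary endpoints.

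**Working it through.** **No figure to reproduce.** The plan gives no effect size, correlation, power or gene count for this comparison. Only the upper limit on pairs comes from the documents: 40 enrolled (11.1), and at most 17 if the trial closes after stage one. Everything else here is assumed.

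**Variance.** With n pairs, equal SD σ at both times and within-patient correlation ρ:

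- true variance of the mean change = 2σ²(1 − ρ)/n
- variance used when pairing is ignored = 2σ²/n
- ratio = 1/(1 − ρ), which is 1.43 at ρ = 0.3, 2.00 at 0.5 and 3.33 at 0.7

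For positive ρ the assumed variance is too large. In simulation with 34 pairs, a nominal 0.05 two-sample test has true size 0.0198, 0.0065 and 0.0007 at these three correlations. The error is lost power, not extra false positives.

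**Yield at FDR 0.05.** Assumptions: 15,000 independent genes, 1,500 of them shifted, normal data, Benjamini-Hochberg at 0.05, two-sample t test against paired t test, 20 runs per cell. On the number of pairs, 40 is the maximum. The value 34 is 40 × 0.85, which is what remains if 15% of patients have no residual tumor; 15% is the complete-response fraction at which 9.2.3 switches comparison. The value 20 is a low case. Mean true findings at ρ = 0.3 / 0.5 / 0.7:

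| Pairs | Shift | Pairing ignored | Paired |
|---|---|---|---|
| 20 | 0.5 SD | 0.3 / 0.1 / 0 | 4.8 / 33 / 351 |
| 20 | 0.8 SD | 138 / 53 / 12 | 450 / 868 / 1,356 |
| 20 | 1.0 SD | 697 / 691 / 701 | 997 / 1,311 / 1,487 |
| 34 | 0.5 SD | 6.3 / 0.7 / 0 | 180 / 505 / 1,109 |
| 34 | 0.8 SD | 902 / 949 / 992 | 1,192 / 1,416 / 1,497 |
| 34 | 1.0 SD | 1,374 / 1,417 / 1,460 | 1,449 / 1,494 / 1,500 |
| 40 | 0.5 SD | 35.5 / 2.8 / 0.1 | 339 / 728 / 1,270 |
| 40 | 0.8 SD | 1,124 / 1,192 / 1,283 | 1,330 / 1,462 / 1,500 |
| 40 | 1.0 SD | 1,450 / 1,473 / 1,493 | 1,484 / 1,499 / 1,500 |

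Repeat runs agree within simulation error. The smallest cells are noisy.

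Loss = 1 − (pairing ignored / paired). With 34 pairs at 0.8 SD and ρ = 0.3, this is 1 − 902/1,192 = 24%; across the three correlations it is 24-34%. With 20 pairs at 0.8 SD it is 69-99%. At 1.0 SD with 34 to 40 pairs it is 0.5-5%.

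**Zero correlation.** Pairing then costs power. True findings, paired against pairing ignored:

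- 34 pairs, 0.8 SD: 794 against 880, a cost of 86/880 = 10%
- 34 pairs, 1.0 SD: 1,275 against 1,321, a cost of 46/1,321 = 3%
- 20 pairs, 0.8 SD: 134 against 241, a cost of 107/241 = 44%

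**Counts instead of normal data.** With simulated Poisson-lognormal counts and 34 pairs, t tests on log counts give losses of 32-50% at about 0.77 SD and 7-9% at about 0.96 SD. None of these are CuffDiff2 runs; they approximate a group test.

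**The case against.** The strongest reply is that silence is not a wrong method. The pre/post sentence names no test. The account of CuffDiff2 is a summary that refers to reference 71 for detail, and CuffDiff2 is not the only test in 11.3. This stands in part: applying CuffDiff2 to the pre/post comparison is an inference. It is the natural one, because 11.3 names that program for the analysis and 9.2.2 says that it tests the differences.

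A reader might go further and infer that the plan prescribes an unpaired pre/post test, since 11.3 contains the words "will be compared using an unpaired t test on all probes". The documents do not support that. Those words apply to complete responders against other patients. These are different people, so an unpaired test is suitable there. Nor do the documents show that CuffDiff2 cannot handle pairs.

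A second reply is that the size is assumed and some percentages flatter the point. This stands. At 0.5 SD the relative losses exceed 90% in most cells, but with 20 pairs and correlation 0.3 that means 0.3 against 4.8 genes out of 1,500. For large shifts with many pairs little is lost. With about 20 pairs and no correlation, pairing does worse. Positive correlation is still the reasonable expectation for two samples of one patient's tumor.

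A third reply is that the work is exploratory and the error conservative. That limits the weight of the point but does not remove it: 11.3 is the statistical section for this objective, and the choice is better made before the data are seen.

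**Conclusion.** The point holds as a gap with a clear remedy. The samples are matched, no pairing is stated, and the program named is described without a patient term. Followed as written, the plan gives a less sensitive test for objective 2.2.8 wherever within-patient correlation is positive.

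The loss could be negligible (large shifts, 34 to 40 pairs), about a quarter to a third of true findings (0.8 SD, 34 pairs), or most of them (0.8 SD, 20 pairs). Which applies depends on correlation, effect size and number of complete pairs, none of which the documents give. There is no case here for excess false positives.

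**What to change.** In 9.2.2, 9.2.4 and 11.3, state that the pre/post comparison is made within patient. Use a count-based model with patient as blocking factor and time (pre, post) as the tested term, at FDR below 0.05. Keep CuffDiff2 for this comparison only if it is confirmed to support that. Otherwise use a negative-binomial model, or a precision-weighted linear model on log counts. Restrict the comparison to patients with both samples, report the number of complete pairs, and state that pairs exist only where residual tumor remains.

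The cost is a few sentences and possibly a change of software; no new samples are needed. The result applies only to patients with residual tumor. Genes with near-zero within-patient correlation lose power: little with 34 to 40 pairs at 0.8 SD or more, substantially with about 20 pairs.

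As a separate wording matter, 9.2.7 should say whether its p < 0.05 is FDR-adjusted and which comparison it refers to. The pairing point does not depend on this.

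### The complete-responder gene-expression contrast is given two conflicting methods and no data scale; a t test on untransformed FPKM with few responders would not hold the stated 5% FDR

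*Combined protocol and SAP*

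**What the plan says.** Section 9.2.2 sets the assay and its purpose: "We will perform global gene expression profiling using RNAseq to identify differential expression patterns that correlate with response to radiation". It then says "Cufflinks produces FPKM (fragments per Kb of exon per million fragments mapped) values for all transcript isoforms", and that CuffDiff2 tests differences in transcript abundance, "taking into account variance between biological replicates and correction for false discovery rate". Section 11.3 repeats the assignment ("Analysis will be performed using the CuffDiff2 program, part of a commercially available Cufflinks package") and describes the model behind it: "The result is a beta negative binomial distribution that reflects both the sources of variability in an isoform's measured expression level".

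For the contrast between response groups, section 9.2.3 names a different test: "Expression of genes from patients with pathologic complete response versus non-complete responders will be compared using an unpaired t test on all probes". Section 11.3 repeats it: "will be compared using an unpaired t test on all probes, with a false-discovery rate (FDR) of less than 0.05". If fewer than 15% of patients have a complete pathologic response, partial response is compared with no response; 11.3 adds that this is done in a similar manner.

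Neither section says which method governs this contrast, which values enter the t test, whether they are log-transformed, whether variances are pooled, or how the FDR is computed.

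**The concern.** The word *probes* comes from microarrays, and the plan describes no probe-based expression assay. The t-test sentence therefore does not fit the data, and it stands beside a count model written for overdispersed counts.

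The only expression measure the plan names is FPKM. It is right-skewed, and its spread rises with its mean. A t test on such values is sensitive to unequal group sizes, and this contrast may be very unequal. An FDR rule works in the far tail of the p-values, where the error is greatest.

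At stake is the credibility of the gene list for objective 2.2.8, which correlates expression with pathologic response. It may also feed the signature work in 9.2.7. An unstated choice among several analyses, each giving a different list, also leaves room to choose after seeing the data.

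**Working it through.** **1. Smallest responder group.** 15% of 40 is 6.0, and 15% of 39 is 5.85. Five responders (12.5% or 12.8%) trigger the fallback; six (15.0% or 15.4%) do not. So the main contrast can run at 6 v 33 or 6 v 34, if every patient has usable tissue.

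**2. The plan's own figure.** FDR below 0.05 is a target. The plan gives no dispersion, effect size, gene count, scale or variance form, so it cannot be reproduced and has to be tested under assumptions.

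**3. Hand check of direction.** Assume CV 0.8 and a 3-fold change. Set the larger group's mean to 1, with SD equal to CV × mean, and ignore counting noise. At 6 v 33, √(1/6 + 1/33) = 0.444. The expected t is the difference divided by its standard error (SE).

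- Raw, pooled, gene up in responders: SE = 0.8 × √((5×9 + 32)/37) × 0.444 = 0.512; t = 2/0.512 = 3.90.
- Raw, pooled, gene down: SE = 0.8 × √((5/9 + 32)/37) × 0.444 = 0.333; t = 0.667/0.333 = 2.00.
- Raw, Welch, up: SE = 0.8 × √(9/6 + 1/33) = 0.990; t = 2.02.
- Raw, Welch, down: SE = 0.8 × √((1/9)/6 + 1/33) = 0.177; t = 3.77.
- Log, pooled, either direction: SD = √ln(1 + 0.64) = 0.703; t = 1.099/(0.703 × 0.444) = 3.52.

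Pooling penalises genes lower in the small group; Welch penalises genes higher in it. The pooled formula gives 3.98 up and 2.80 down at 12 v 28 (log scale 4.53). At 20 v 20 it gives 3.54 both ways, against 4.94 on the log scale, so power is lost even with equal groups.

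**4. Why the FDR fails.** For lognormal values the skewness is 3CV + CV³ = 2.4 + 0.512 = 2.912. The skewness of the difference in means is 2.912 × (1/n₁² − 1/n₂²)/(1/n₁ + 1/n₂)^1.5. This is 0.90 at 6 v 33, 0.40 at 12 v 28 and 0 at 20 v 20. A null simulation of 400,000 genes at 6 v 33 agrees: false positives at p < 0.0001 were 4.1 to 8.0 times nominal on the raw scale (CV 0.5 to 1.2, pooled variance) and about nominal on the log scale.

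**5. Simulation at 6 v 33.** Assumptions: 15,000 independent genes, 600 changed 3-fold (half up, half down in responders), lognormal variation plus Poisson noise, Benjamini-Hochberg at 0.05. Entries are for CV 0.5 / 0.8 / 1.0.

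| Reading of the t test | Realised FDR, % | Power, genes up, % | Power, genes down, % |
|---|---|---|---|
| Raw, pooled | 8.8 / 13.8 / 16.9 | 98 / 63 / 38 | 40 / 0.4 / 0 |
| Raw, Welch | 26 / 40 / 44 | 9 / 2 / 0.5 | 91 / 64 / 45 |
| Log, pooled | 4.8 / 5.3 / 5.1 | 96 / 48 / 20 | 94 / 45 / 20 |
| Log, Welch | 11 / 17 / 23 | not tabulated | not tabulated |

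Repeat runs of the raw pooled test gave FDRs of 8/13/19% and 8.9/15.3/20.2%. A moderated test on log counts held 4 to 5% with balanced power, and had more power than the t test at every split tried from 6 v 33 to 20 v 20.

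**6. Other splits and a second model.** Here 6,000 genes had gamma or lognormal variation with dispersion 0.3 or 0.8 (CV about √0.3 = 0.55 or √0.8 = 0.89), at 35 million mapped reads. The plan's own depth is 150 to 180 million reads per lane ÷ 4 libraries × 0.875 = 33 to 39 million per sample. Raw pooled results:

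| Responders v others | FDR, % | Power up, % | Power down, % |
|---|---|---|---|
| 6 v 33–34 | 5.8–15.3 | 48–93 | 1–48 |
| 8 v 32 | 5.9–9.4 | 51–95 | 4–58 |
| 10 v 29 | 4.5–6.2 | 49–97 | 7–79 |
| 12 v 28 | 4.0–4.9 | 52–96 | 14–80 |
| 34 v 6 | 7.6–14.5 | 1–38 | 47–91 |

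At about 20 v 20 the FDR was 2.2 to 4.3%, with up and down power within 4 points. In the lognormal case with dispersion 0.8, power there was 52% on the raw scale against 79 to 82% on the log scale. Raw Welch at 6 v 33–34 gave an FDR of 18 to 48%. The pooled test on log2(FPKM+1) gave 4.6 to 5.8%.

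**The case against.** The strongest reply is that the plan never says the t test is run on untransformed FPKM. An unpaired t test on log values is equally compatible with the text and, with pooled variance, holds the FDR near 5%. This stands, and it makes the error rates conditional. It does not remove the conflict between methods or the missing scale.

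A reader might infer that the stated FDR simply fails, or that genes lower in responders are always the ones missed. The documents support neither. The direction needs pooled variance and responders in the minority; it reverses under Welch, or if responders are the larger group, which the fallback contrast could produce. Six responders is the worst case for the main contrast, and pooled FDR is back near 5% by 12 v 28.

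One could also read the sections as a division of labour: CuffDiff2 for pre- versus post-radiation, the t test for response groups. The plan does not say so, and 9.2.2 introduces the CuffDiff2 pipeline for patterns that correlate with response.

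Finally, that the signature in 9.2.7 would inherit the error is an inference. That section applies its own p < 0.05 focus and leaves validation to future studies.

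**Conclusion.** The concern holds as an internal conflict with a conditional consequence. The named t test does not fit the assay, competes with the named software, and lacks the two details that decide how it behaves. At the smallest group the plan allows, the possible readings of one sentence give FDRs from about 5% to about 45%, and gene lists that differ in direction.

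The sizes rest on assumed CVs, 3-fold changes, independent genes and Benjamini-Hochberg adjustment, none of which the plan gives. The log scale balances power under lognormal variation. In the second model, which includes gamma variation, it narrows the gap without closing it: at 6 v 33–34, 79–92% up against 61–83% down at dispersion 0.3, and 26–58% against 8–36% at dispersion 0.8. CuffDiff2 itself was not run, so nothing here measures its performance.

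This is a translational analysis under objective 2.2.8. It should be corrected, but it does not touch the primary endpoint or the sample size.

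**What to change.** In 9.2.3 and 11.3, replace the t-test-on-probes wording with one named gene-level procedure for the responder contrast. Either a moderated linear model on log counts with precision weights, or one count-based model such as the CuffDiff2 analysis already named, would resolve the conflict. State Benjamini-Hochberg FDR 0.05 across all genes passing an expression filter fixed in advance. State that the same procedure applies to the partial versus no response fallback.

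If the sponsor prefers to keep a t test, the text must at least give the log scale and pooled variance; Welch on the log scale gave an FDR of 11 to 23% at 6 v 33.

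The cost is about two sentences in the two places, using free standard software. No new data are needed.
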